#### 10.4.11 EXPLORATORY ANALYSES

None

### 10.5 SAMPLE SIZE

The most efficient approach to performing the power calculation for this study via Monte Carlo simulation as the underlying phenomenon, AK rate, is best modeled by a Poisson distribution.

As a starting point, we took the distribution of AK rates from actual clinical data. The data were assembled by querying EPIC on 2014 visits of kidney transplant patients to dermatology (this subset of the population will have fewer AK's than the non-transplant subjects and therefore use of this distribution will err on the side of caution toward overpowered the study). For each visit in which the dermatologist chose to treat by LN2 destruction, the query retrieved the number of procedures performed. This approach is conservative as the input data potentially underestimates AK count as some AK's may not have been treated.

The structure of the Monte Carlo was straightforward. A set of potential study sizes (N recruited) and effect sizes were chosen. For each input condition, two thousand random experiments were performed. In each of these interactions, baseline AK rates were drawn from the clinically observed distribution of AK's. Subjects were sequentially assigned to treatment or control groups. Observed AK rates were generated using a Poisson distribution for each visit. The analysis expected for the study was then performed. In this analysis the total count of AK's for each subject was obtained and the means and distributions compared for directionality (AK\_treated < AK\_control) and significance (p-value from a one-tailed t-test).

Analysis was performed in R (R Open 3.2.3) with statistical calculations and random number generation using the base and stat libraries.

[figure not shown]

Figure 10.5.1. With an effect size of 0.25 and recruitment of 100 patients (50 treatment, 50 control) we predict a power of 0.81.

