## 4 STUDY DESIGN AND ENDPOINTS

### 4.1 DESCRIPTION OF THE STUDY DESIGN

This randomized partially blinded study will recruit 120 patients with a history of actinic keratosis (AK) lesions. A control versus study group analysis will be performed where 50% of the subjects will be randomly assigned (balanced by Fitzpatrick skin type, separate randomization lists will be made for type I&II and types III-VI, at time of first visit subjects will be assigned to study or control group by giving them the next assignment on the appropriate list) to use the SHADE sensor and its app (study group), while the other 50% (control group) will receive standard of care UV counseling(placebo). Subjects will have 3 visits. The first and last visit will be standard of care visits at 0 month (enrollment), and the conclusion of their involvement. The second visit will be scheduled 3 months after the enrollment visit. The final visit will be scheduled as soon as practical, but at least 3 months after visit 2 and after September 30. On arrival at each visit, study personnel will pre-screen patients to ensure that the sensor is not visible to physician prior to examination, for example by placing it in their pocket. At each follow up visit, the number of actinic keratosis on the face and hands will be counted and photographed. They will be treated as per standard of care protocol with cryotherapy or curettage. General use of field therapies will not be permitted during the trial. Any lesions suspicious of non-melanoma or melanoma skin cancer will be photographed and biopsied as part of the standard of care algorithm. Cyclobutane pyrimidine dimers (CPD) levels will be measured by ELISA from exposed (cheek) and unexposed (buccal mucosa) skin scrapings collected at the first and last visit. For each patient, the CPD level from exposed skin will be normalized to the sun protected CPD level measured from unexposed skin. We will compare the normalized CPD level of control versus study participants at each timepoint and their average CPD change over time.

We will then compare these levels with Shade UV measurements. Finally, patients will also answer questions in PROMIS (Patient-Reported Outcomes Measurement Information System) in the fields of anxiety, depression and ability to participate socially to gauge their attitudes toward the sensor

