#### 10.4.1 GENERAL APPROACH

All tests will be two-tailed with the significance level set at 0.05. Analysis will be performed using STATA statistical software (StataCorp. 2015) or R (R: A language and environment for statistical computing. R Foundation for Statistical Computing, Vienna, Austria).

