### ***17.2 MANAGING PROTOCOL CHANGES FOR CONTINUING SUBJECTS***

All subjects who signed consent forms prior to the protocol change will be reconsented at their next visit.

Visits one and two are unchanged. Visits 3 and 4 have been removed from the protocol. At the time of this protocol change some subjects have completed visit 2. These subjects, who were scheduled to have a visit that is no longer part of the study design will be informed that this visit is no longer required. As no action is required of these subjects there will be no need to reconsent until their final study visit. For subjects who have not yet had their 3 month visit, reconsent at visit 2 will be appropriate.

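### The 0.81 power in section 10.5 is not tied to the current design: it sums per-visit counts over an unstated number of visits, and the schedule has since been cut to two follow-up visits

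*Combined protocol and SAP*

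**What the plan says.** Section 10.5 (Sample Size) describes a Monte Carlo calculation. For each simulated patient, "baseline AK rates were drawn from the clinically observed distribution of AK's". Then "Observed AK rates were generated using a Poisson distribution for each visit", and "In this analysis the total count of AK's for each subject was obtained". The arms are compared by a one-tailed t-test. The result is: "With an effect size of 0.25 and recruitment of 100 patients (50 treatment, 50 control) we predict a power of 0.81". The section does not give the number of visits simulated, the follow-up time, the significance level, or the mean and spread of the AK distribution.

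Section 17.2 reports a change of schedule: "Visits one and two are unchanged. Visits 3 and 4 have been removed from the protocol". Section 4.1 now reads "Subjects will have 3 visits": enrollment, a visit at three months, and a final visit at least three months later and after 30 September. Because section 10.4 counts only lesions that arise after the first visit, two counting visits remain. Section 4.1 also sets recruitment at 120.

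Section 10.4.1 adds: "All tests will be two-tailed with the significance level set at 0.05".

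**The concern.** In the model of section 10.5, the expected total per patient is the per-visit rate times the number of visits. A smaller total carries more Poisson noise relative to its mean, so with rates held fixed, fewer visits mean lower power. The schedule has been shortened, and nothing says which schedule the simulation used.

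Several places still reflect a longer design: the 12-month period in section 2.2, the quarterly visits in 5.4.1, the t12 index in the hypotheses of 10.4.2 and the 12-month CPD column in 10.4.10. The simulated size (100) also differs from the planned size (120).

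The 0.81 is the only quantitative support for the trial size. If it describes another schedule, readers cannot judge what a null result means.

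**Working it through.** **Inputs.** From 10.5: 50 per arm, effect 0.25 (read as a 25% lower rate), power 0.81, one-tailed test. From 4.1: 120 patients, so 60 per arm. From 10.4.1: two-tailed 0.05. Assumed: one-tailed level 0.05 in 10.5; four follow-up visits behind the 0.81.

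**Reproducing 0.81.** This cannot be done independently, because visit count, mean and spread are not given. The figure can only be used to calibrate.

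**Formula.** Let T be the expected control total and c the between-patient coefficient of variation of the AK rate. The control variance is T + c²T², and the treated variance is 0.75T + c²(0.75T)². With n per arm,

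power = Φ(0.25/√(S/n) − z), where S = 1.75/T + 1.5625c².

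**Calibration.** Power 0.81 at n = 50, one-tailed 0.05, needs 0.25/√(S/50) = 1.645 + 0.878 = 2.523. So S = 50 × 0.0625/2.523² = 0.491. It follows that T is at least 1.75/0.491 = 3.56 and c at most √(0.491/1.5625) = 0.56.

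**Range of T.** Section 10.5 took its data from visits at which lesions were treated, so each sampled visit should have at least one procedure. A four-visit total of 4 would then mean exactly one at every visit and no between-patient variation, which does not fit the calibrated c of 0.19. The range shown therefore starts at 6.

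**Worked case, T = 12.** 1.75/12 = 0.146, so 1.5625c² = 0.491 − 0.146 = 0.345 and c = 0.47. Halve the total: S = 1.75/6 + 0.345 = 0.637. At n = 60, 0.25/√(0.637/60) = 2.43. Power is Φ(2.43 − 1.645) = 0.78 one-tailed and Φ(2.43 − 1.960) = 0.68 two-tailed.

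**Results.** Each cell shows power if the total halves / falls by a quarter.

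| Four-visit mean T | c | 50 per arm, one-tailed | 60 per arm, one-tailed | 60 per arm, two-tailed |
|---|---|---|---|---|
| 6 | 0.36 | 0.64 / 0.75 | 0.71 / 0.81 | 0.59 / 0.71 |
| 8 | 0.42 | 0.67 / 0.76 | 0.74 / 0.82 | 0.63 / 0.73 |
| 12 | 0.47 | 0.72 / 0.78 | 0.78 / 0.84 | 0.68 / 0.75 |
| 20 | 0.51 | 0.75 / 0.79 | 0.82 / 0.85 | 0.72 / 0.77 |
| 40 | 0.53 | 0.78 / 0.80 | 0.84 / 0.86 | 0.75 / 0.78 |

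With the total unchanged, S stays at 0.491. Power is then 0.81 at 50 per arm and 0.87 at 60 per arm one-tailed, or 0.71 and 0.79 two-tailed.

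A gamma-Poisson simulation with a t-test (20,000 replicates) agrees. For T = 12 halved it gives 0.71 at 50 per arm, and 0.78 one-tailed and 0.68 two-tailed at 60 per arm.

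**What the scenarios correspond to.** If new lesions accrue in proportion to time, going from 12 to 6 months halves the total and going from 12 to 9 months cuts it by a quarter. The documents allow all of these: at least about six months in 4.1, 9-12 months in 6.1.9, 12 months in 2.2 and one summer in the Protocol Summary.

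**The case against.** A reader might infer that 0.81 was computed for four follow-up visits and that removing two has left the trial underpowered. The documents do not support that.

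- **The visit count is inferred.** Removing visits 3 and 4 while three remain points to five visits before, hence four follow-ups, but no section states this or dates the simulation. Section 17.2 is change-history text; its difference from the current schedule is not an error. Two visits also give 0.81, for example with a mean of 3 per visit and c = 0.36, or 5 per visit and c = 0.45.
- **The signs of age are mixed.** Section 10.5 already mentions non-transplant patients, and 10.4.10 lists three PROMIS visits. Section 10.5 says several study sizes were simulated, so a result read at 100 does not date the run.
- **Follow-up time matters, not visit number.** If total time is unchanged, lesions are counted later rather than lost. Two visits with double the count per visit again simulate to 0.81.
- **The larger sample offsets some or all of the loss.** At 60 per arm, one-tailed power is at least 0.81 throughout the range shown if the total falls by a quarter. If it halves, power reaches 0.82-0.84 for T of 20 to 40.

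All four points stand, and they rule out calling this a demonstrated power error. They do not tie 0.81 to the current design. The offset also relies on the one-tailed test, which is not the planned one, and on all 120 being analysed. Section 10.4.2 excludes patients with sensor use on fewer than 15% of days, and 5.4.2 restricts each analysis to complete data.

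**Conclusion.** The point holds as a gap in the sample-size justification: 0.81 cannot be read as the power of the current trial. The visit count and follow-up time behind it are unstated, the schedule has changed, and both the size and the test differ from those planned.

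Whether the visit change alone costs power cannot be settled from the documents. If the simulation already used the current visits and follow-up time, that change costs nothing. The size of any loss depends on the assumed four visits, a gamma or similar mixed-Poisson model, one-tailed 0.05 in 10.5, and four-visit means of 6 to 40.

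One result does not need the visit count. Calibrated to 0.81 at 50 per arm, two-tailed power at 60 per arm is about 0.79 even with no loss of counts, and exclusions would lower it further.

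**What to change.** Rerun the existing R simulation for the design as it now stands: counts at V2 and V3, rates scaled to the actual follow-up time, 60 per arm, two-tailed 0.05. The statements of study duration in the Protocol Summary and sections 2.2, 4.1 and 6.1.9 must be reconciled first, since the scaling depends on them.

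Replace 0.81 and figure 10.5.1 with the result. State in 10.5 the number of visits, the follow-up time, the mean and SD of the AK distribution, and the significance level. Keep 120 patients.

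The cost is one rerun and a short edit to 10.5. It needs no trial outcome data. The downside is that the stated power may become less favourable.

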#### 10.4.2 ANALYSIS OF THE PRIMARY EFFICACY ENDPOINT(S)

##### **#1 (Primary): Quantify the impact of Shade on the cumulative number of new actinic keratoses developed over the study period.**

To test our primary aim, we will perform a control versus study group analysis. The study group will receive a Shade sensor and Shade app while the control group will standard of care sun avoidance counseling. The study will be randomized and single-blinded as described in section 10.6.1. This will also allow us to control for the effect of UV level variation on the primary outcome since the two groups will have balanced enrollment dates. All the patients will receive recommendations about UV exposure protection as defined by the recommendations of the American Academy of Dermatology and the National Cancer Institute.

Patients who will have used the Shade sensor for less than 15% of the days over the study period will be excluded from these analyses. We will use a Student's t-test with the following null and alternative hypothesis:

$$H_0: \text{mean}^C_{t12} (\text{AK}) = \text{mean}^I_{t12} (\text{AK})$$

$$H_a: \text{mean}^C_{t12} (\text{AK}) \neq \text{mean}^I_{t12} (\text{AK})$$

where  $\text{mean}^C_{t12} (\text{AK})$  is the averaged cumulative number of AK between enrollment follow up of controls and  $\text{mean}^I_{t12} (\text{AK})$  is the averaged cumulative number of AK of intervention patients.

In this analysis, demographic and clinical factors such as gender, age, baseline count of AKs, skin type, immunosuppressive treatment and comorbidity can be confounding factors. To test and control for confounding, demographic and clinical data (skin type, living area, gender, age, count of AK at enrollment, immunosuppressive (IS) treatment, level of immunosuppression and comorbidity) will be collected. We will use a stepwise multivariate approach with backward selection: 1) the effect of potential confounding factors will be tested using the same statistical tests, 2) factors with p-value <0.2 and less than 25% of missing values will be included in the multivariate model and 3) only covariates with significant adjusted p-value (<0.05) will be kept in the final model. Clinically relevant interactions will also be tested (e.g. skin type, gender, age) and kept in the final model if significant. The adjusted effect of Shade use will be estimated using a multivariate linear regression.

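### The 0.81 power in section 10.5 comes from a one-tailed t-test with no stated cut-off, while 10.4.1 and 10.4.2 plan a two-tailed test at 0.05

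*Combined protocol and SAP*

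**What the plan says.** **The power statement (10.5).** The simulation covered several sizes and effects: "A set of potential study sizes (N recruited) and effect sizes were chosen". Each condition had 2000 replicates. Patient rates came from clinic data, and "Observed AK rates were generated using a Poisson distribution for each visit". Then: "The analysis expected for the study was then performed". That analysis compared the arms on direction and on a "p-value from a one-tailed t-test". The caption of Figure 10.5.1 gives the result: "With an effect size of 0.25 and recruitment of 100 patients (50 treatment, 50 control) we predict a power of 0.81".

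**The planned test.** Section 10.4.1: "All tests will be two-tailed with the significance level set at 0.05". Section 10.4.2, for the primary endpoint: "We will use a Student's t-test with the following null and alternative hypothesis". The alternative shown there is that the two means are unequal.

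**Related places.**
- Section 10.2 words the null directionally (damage with the sensor no lower than without it), then defers to the more precise hypotheses that follow.
- Section 4.1 plans 120 patients, 1:1, with three visits, two of them after enrolment.
- Section 10.4.2 drops patients who used the sensor on fewer than 15% of days, and 5.4.2 keeps only complete data for each endpoint.
- Section 17.2 records that visits were taken out of the design.

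**The concern.** Section 10.5 presents its simulated test as the one the study will use, but the simulated test is one-tailed and the planned test is two-tailed. A one-tailed test at 0.05 rejects more easily in the expected direction than a two-tailed test at 0.05. Its power therefore cannot be carried over unless the one-tailed cut-off was 0.025, and the readable text does not say which was used. The only significance level it sets for the study's tests is 0.05.

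At stake is whether the sample-size section establishes the power of the primary analysis. The caption speaks of 100 recruited, the plan recruits 120, and the readable text neither gives a power at 120 nor explains the step between them.

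**Working it through.** **Inputs from the documents.** Power 0.81 at 50 per arm, one-tailed t-test, 2000 replicates (10.5). Two-tailed 0.05 (10.4.1, 10.4.2). 60 per arm (4.1). The effect size of 0.25 is read as the 25% reduction in 10.4. The AK distribution and the simulation cut-off are not in the readable text, so 0.81 cannot be rebuilt from its own inputs. It can only be converted.

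**Step 1: standardized difference d implied by 0.81 at 50 per arm.** By the normal approximation, d = (z for the cut-off + z for 0.81) / √(50/2), where √25 = 5.
- Cut-off 0.05: (1.645 + 0.878)/5 = 0.505. Noncentral t: 0.508.
- Cut-off 0.025: (1.960 + 0.878)/5 = 0.568. Noncentral t: 0.573.

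Putting each d back into the one-tailed test at 50 per arm returns 0.81.

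**Step 2: power of the planned two-tailed 0.05 test.** Power = Φ(d√(n/2) − 1.960), with n per arm. At n = 60, √30 = 5.477.
- Cut-off 0.05, N = 100: Φ(2.523 − 1.960) = 0.713.
- Cut-off 0.05, N = 120: Φ(2.763 − 1.960) = 0.789.
- Cut-off 0.025, N = 100: 0.81, unchanged.
- Cut-off 0.025, N = 120: Φ(3.109 − 1.960) = 0.875.

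| Simulation cut-off | Two-tailed 0.05 power, N = 100 (noncentral t) | N = 120 (noncentral t) |
|---|---|---|
| one-tailed 0.05 | 0.711 | 0.788 |
| one-tailed 0.025 | 0.810 | 0.876 |

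**Step 3: simulation error in 0.81.** The standard error is √(0.81 × 0.19 / 2000) = 0.0088, so 0.81 could be 0.793 to 0.827. At N = 120 this maps to 0.768 to 0.808 (cut-off 0.05) or 0.861 to 0.890 (cut-off 0.025). At N = 100 with cut-off 0.05 it maps to 0.689 to 0.733.

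**Step 4: does the conversion hold for counts?** Gamma-mixed Poisson counts were simulated with a 25% reduction, two visits and assumed means of 3, 5 and 8 AKs per visit. The spread was tuned so that one-tailed power at 50 per arm was 0.81. Two-tailed power at N = 120 was 0.77 to 0.79 (cut-off 0.05) or 0.87 (cut-off 0.025). This supports the t conversion. It cannot test whether the simulated design matches the current one, because every case was tuned to 0.81.

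**Step 5: sensitivity to losses and visits (assumptions, not plan figures).**
- If 108 are analysable, evenly split, power is 0.74 or 0.84. If 100 are, it is 0.71 or 0.81.
- Suppose four follow-up visits were simulated and two are now held. With mean m per visit, V visits and gamma shape k, d = 0.25Vm / √{½[Vm + (Vm)²/k + 0.75Vm + (0.75Vm)²/k]}. For m = 2 and cut-off 0.05, k = 5.89 gives d = 0.508 at V = 4 and 0.422 at V = 2, hence power 0.63 at N = 120. For m from 2 to 8, power at 120 is about 0.63 to 0.74 (cut-off 0.05) or 0.70 to 0.83 (cut-off 0.025).

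**The case against.** **The cut-off may have been 0.025.** Then 0.81 already describes the planned test and 120 patients give more. Section 10.5 also checks direction separately from the p-value, which a one-tailed p-value at 0.05 would make redundant, so the script may have done something other than the prose suggests. This stands as a possibility, and it is why the consequence is conditional. It does not reconcile the wording.

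**Figure 10.5.1 could not be read here.** It may show the cut-off and the power at 120. That limits this point to the text and caption, but a figure would not remove the conflict in the prose.

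**The step from 100 to 120 may be an allowance for losses.** It is a 20% increase, and 10.5 speaks of patients recruited. The readable text does not say so, nor whether losses were simulated.

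**The inputs are called conservative.** Section 10.5 says: "This approach is conservative as the input data potentially underestimates AK count as some AK's may not have been treated". This is not quantified, and it has no bearing on which test was run.

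**The adjusted regression in 10.4.2 could raise power** by using the baseline AK count. That is possible, but the hypothesis stated there is tested by the t-test, and that is also what was simulated.

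**Stronger readings to avoid.** A reader might infer that the trial is underpowered, or that its true power lies between 0.79 and 0.88. The documents support neither. One cut-off gives a gain, the plan names no target power, and Step 5 shows values outside that range if the visit count has changed. Nor is the false-positive rate inflated, since the planned test itself is unchanged.

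**Conclusion.** Wrong as written, with modest impact. The mismatch between a one-tailed simulation and a two-tailed plan is plain in the text. What it costs is not.

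Under a one-tailed 0.05 cut-off, 0.81 overstates the planned test's power at 100 by about 10 points (0.71). At 120 the power is about 0.79, some 2 points below the stated figure. Under 0.025 there is no loss at 100 and power is about 0.88 at 120.

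The values for 120 rest on three assumptions: all 120 are analysed, the simulation made no allowance for losses, and it used the two follow-up visits in 4.1. If some patients are excluded and no allowance was simulated, power is lower. If more visits were simulated than are now held, it is lower still.

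**What to change.** 1. Rerun the existing R simulation with the 10.4.2 test (Student's t-test, two-tailed, 0.05), the two follow-up visits in 4.1, and a stated analysable number out of 120 after the 15%-use exclusion and the complete-data rule in 5.4.2.
2. Replace the 0.81 sentence in 10.5 with, for example: *For a 25% reduction, with [n] analysable of 120 recruited, two follow-up visits and a two-tailed Student's t-test at 0.05, simulated power is [rerun result].* The text should name the test and cut-off even if the figure shows them.
3. Align the directional null in 10.2 with 10.4.1 and 10.4.2.

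The cost is one rerun, three short edits and a stated power that may be less favourable. No added enrolment is needed.

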## 10.6 MEASURES TO MINIMIZE BIAS

This study will be partially blinded. We will divide study participants into 2 groups. The experimental group will wear an ultraviolet sensor which will record their UV exposure. The control group will receive standard of care counseling about photoprotection from their dermatologist. The study coordinator will spend the first 10 minutes of the visit with each patient reviewing any issues related to the study, including sensor related issues. The study coordinator will remind the patient at each visit to put the sensor away from view and to not discuss any sensor related questions to the dermatologist. The dermatologist will then come in and perform a total body skin examination. Actinic keratosis will be identified, circled and photographed. The actinic keratosis will then be treated via a destruction method. Any potential skin cancers will be biopsied and sent for pathology. Cyclopyridimine butane dimer (CPD) analysis will be obtained via light curettage of the skin and mucosa. They will be sent to a lab and the data will be processed. A different physician will evaluate the results and will not have access to clinical data. This physician will remain completely blinded to the study.

